4.5.2. Safety Variables

1. The secondary outcome measures will be:
 - a. Incidence and severity serious adverse events reported at any time from the time of study treatment through the end of the study.
 - b. Incidence and severity of related adverse events reported at any time from the time of study treatment through Day 12.
 - c. Summary of physical examination findings (height at baseline, and weight at serial time points from Day of Admission until Day 12), vital signs (serial time points from Day of Admission until Day 12), safety laboratory parameters (Day of Admission, as well as Days 2, 5, and 12), and ECG data (Day of Admission and Day 12).

5. SAMPLE SIZE CONSIDERATIONS

The sample size was determined based on feasibility and FDA guidance (12). Following FDA guidance, enrollment is anticipated to include at least 6 subjects in each arm. This sample size is expected to estimate the group differences with adequate precision. Previous studies of Pretomanid have estimated coefficients of variation (CV) of <21% after 250 mg dosing (N=8) and <33% after 200 mg dosing (N=6) for single dose $AUC_{(0-\infty)}$ and C_{max} in healthy adult subjects (11). Assuming an observed two-fold difference between the group with severe hepatic impairment and matched controls with no correlation between matched pairs and a coefficient of variation of 25%, a 90% confidence interval for the fold difference between severely impaired and non-hepatically impaired group is (1.55, 2.59).

6. GENERAL STATISTICAL CONSIDERATIONS

6.1. General Principles

All continuous variables will be summarized using the following descriptive statistics: n (non-missing sample size), mean, standard deviation, median, maximum and minimum. The frequency and percentages (based on the non-missing sample size) of observed levels will be reported for all categorical measures. In general, all data will be listed, sorted by impairment group and subject, and when appropriate by visit number within subject. In general, the last recorded value prior to study drug administration will be considered as baseline. All summary tables will be structured with a column for each impairment group in the order (Mild Hepatic Impairment, Moderate Hepatic Impairment, Severe Hepatic Impairment, Matched Controls) and will be annotated with the total population size relevant to that table/impairment group, including any missing observations. More details will be provided for reporting pharmacokinetic results in Section [10](#).

6.2. Timing of Analyses

Two SMC interim safety reviews are planned.

1. After 3 subjects with mild hepatic impairment are enrolled and completed follow-up through Day 12. This review will be completed prior to opening enrollment for subjects with moderate or severe hepatic impairment. Enrollment of subjects with mild hepatic impairment and matched controls may continue during the safety review.
2. After 3 subjects with moderate or severe hepatic impairment are enrolled and complete follow-up through Day 12. Enrollment of subjects with mild hepatic impairment, moderate hepatic impairment, severe hepatic impairment, and matched controls may continue during the safety review.

Each interim safety review will present data by impairment group including AEs, SAEs, clinical laboratory tests, vital signs, PK analysis and 12-lead ECG. Cumulative data for all subjects enrolled will be included in the safety reviews.

Interim safety reviews will not include any statistical hypothesis testing.

The final analysis will be performed after database lock.

6.3. Analysis Populations

Summaries and analysis of safety data will be presented for the Safety Population. Summaries and analysis of pharmacokinetics data will be presented for the Pharmacokinetics Population. A tabular listing of all subjects, visits, and observations excluded from the analysis populations will be provided in the CSR ([Table 7](#); [Listing 1](#); and [Listing 4](#)).

6.3.1. Safety Population

The safety analysis set will include all participants who receive study product.

6.3.2. Pharmacokinetics Population

The PK analysis set will consist of participants in the safety population who have evaluable plasma PK samples for the estimation of C_{\max} or $AUC_{(0-\infty)}$. Subjects may also be excluded from analysis for reasons such

as wrong dose or eating before a dose. What constitutes a reason for exclusion will be assessed on a case-by-case basis by DMID and the VTEU PI.

6.4. Covariates and Subgroups

This study is not powered for formal subgroup analyses and none will be explored.

6.5. Missing Data

All attempts will be made to collect all data per protocol. As missing data are expected to be minimal, no imputation will be performed for missing values. Any data point that appears to be erroneous or inexplicable based on clinical judgment will be investigated as a possible outlier.

6.6. Interim Analyses and Data Monitoring

See Section [6.2](#).

6.7. Multicenter Studies

This study will take place at two VTEU sites, Duke University and St. Louis University. Data will be pooled across both clinical sites except for demographics which will be summarized by site and the comparison of PK parameters will be presented according to site and impairment group (if applicable, as described in Section [10.3](#)).

6.8. Multiple Comparisons/Multiplicity

This study was designed to test the hypothesis that Pretomanid PK parameters following drug exposure will differ between patients with hepatic impairment and non-hepatically impaired controls. This results in three comparisons, however no adjustment for multiple comparisons is planned.

7. STUDY SUBJECTS

7.1. Disposition of Subjects

[Table 8](#) will present a summary of the reasons that subjects were screened but not enrolled.

The composition of analysis populations, including reasons for subject exclusion, by impairment group, is presented in [Table 7](#).

The disposition of subjects in the study will be tabulated by impairment group ([Table 6](#)). The table shows the total number of subjects screened, enrolled, who received treatment, completed all hourly assessments, and the number who completed the Day 12 follow-up.

A flowchart showing the disposition of study subjects, adapted from the Consort Statement ([12](#)) will be included ([Figure 1](#)). This figure will present the number of subjects screened, enrolled, terminated early, and analyzed, by impairment group.

A listing of subjects who are terminated from study follow-up and the reason will be included in [Listing 1](#).

7.2. Protocol Deviations

A summary of subject-specific protocol deviations will be presented by the reason for the deviation, the deviation category, and impairment group for all subjects ([Table 4](#)). All subject-specific protocol deviations and non-subject specific protocol deviations will be included in Appendix 3 as data listings ([Listing 2](#) and [Listing 3](#), respectively).

8. EFFICACY EVALUATION

This study is primarily a pharmacokinetics study and does not include an efficacy evaluation.

9. SAFETY EVALUATION

All summaries and analysis of safety data will be presented for the Safety Analysis Population. Safety summaries will be presented overall and by impairment group.

Listings will be sorted by impairment group, subject ID, parameter (if applicable), and visit (if applicable). Continuous variables will be summarized using the following descriptive statistics: n (non-missing sample size), mean, standard deviation, median, maximum and minimum. All categorical measures will be summarized by the frequency and percentages (based on the non-missing sample size) of observed levels. The denominator for the percentages may be based on the number of non-missing observations for an assessment or based on the number of subjects in a population. This will be described for each table.

9.1. Demographic and Other Baseline Characteristics

Summaries of age, height, weight (measured at screening), sex, ethnicity, and race will be presented by impairment group and overall ([Table 11](#); [Table 12](#)) as well as by site ([Table 9](#) and [Table 10](#)). Ethnicity is categorized as Hispanic or Latino, or not Hispanic and not Latino. In accordance with NIH reporting policy, subjects may self-designate as belonging to more than one race or may refuse to identify a race, the latter reflected in the CRF as “No” to each racial option.

Individual subject listings ([Appendix 3](#)) will be presented for all demographics ([Listing 5](#)).

9.1.1. Prior and Concurrent Medical Conditions

Complete medical history will be obtained by interview of subjects at the screening visit and will be reviewed and/or updated on Day 1 prior to dosage. Subjects will be queried regarding a history of significant medical disorders of the head, eyes, ears, nose, throat, mouth, cardiovascular system, lungs, gastrointestinal tract, liver, pancreas, kidney, urologic system, nervous system, blood, lymph nodes, endocrine system, musculoskeletal system, skin, and genital/reproductive tract. A history of any allergies, cancer, immunodeficiency, psychiatric illness, substance abuse, and autoimmune disease will be solicited.

All current illnesses and pre-existing medical conditions will be MedDRA® coded using MedDRA dictionary version 21.0 or higher. Summaries of subjects’ pre-existing medical conditions will be presented by impairment group ([Table 13](#)).

Individual subject listings will be presented for all medical conditions ([Listing 6](#)).

9.1.2. Prior and Concomitant Medications

Summaries of medications that were started prior to dosing and continuing at the time of dosing will be presented by WHO Drug Terms 2 and 3 and impairment group ([Table 140](#)).

Individual subject listings will be presented for all concomitant medications ([Listing 14](#)).

9.2. Measurements of Treatment Compliance

Any subjects who were enrolled but not dosed will be presented by impairment group as part of the subject disposition table ([Table 6](#)).

9.3. Adverse Events

When calculating the incidence of adverse events (i.e., on a per subject basis), each subject will only be counted once and any repetitions of adverse events within a subject will be ignored; the denominator will be the total population size. All adverse events reported will be included in the summaries and analyses. Adverse event grading scales are presented in [Table 5](#).

An overall summary of adverse events is presented in [Table 14](#).

9.3.1. Unsolicited Adverse Events

The proportion of subjects reporting at least one unsolicited adverse event will be summarized by MedDRA system organ class and preferred term for each impairment group. Denominators for percentages are the number of subjects who received Pretomanid being summarized.

Adverse events by subject will be presented in [Listing 7](#).

The following summaries for unsolicited adverse events will be presented by MedDRA system organ class, preferred term, and impairment group:

- Subject incidence and total frequency of adverse events over time by dose with 95% CI (Days 1-5, Days > 5) ([Table 15](#); [Table 16](#); [Table 17](#); and [Table 18](#));
- Summary of severity and relationship to study product ([Table 19](#));
- Subject listing of non-serious adverse events of moderate or greater severity ([Table 21](#));
- Bar chart of serious and non-serious related adverse events by severity and MedDRA system organ class ([Figure 3](#) and [Figure 4](#)).

9.4. Deaths, Serious Adverse Events and other Significant Adverse Events

The following listings will be presented including Subject ID, Adverse Event Description, Reason Reported as an SAE, Relationship to Treatment, Alternate Etiology if not Related, Outcome, and Duration of Event (days):

- Deaths and Serious Adverse Events ([Table 20](#)).

9.5. Pregnancies

Pregnancy is not considered an adverse event; however, for females, information will be collected for any pregnancies which occur during study drug administration until the Study Day 12 Visit. Male subjects should notify the study team if a pregnancy occurs in a partner within 3 months after study drug administration. If the male subject reports a pregnancy, information about complications during pregnancy, labor and delivery, or congenital birth defects will be collected from the male subject's female partner using a site-specific Pregnant Partner Information and Authorization form. Certain pregnancy outcomes (congenital anomaly or birth defect in an offspring of a subject taking study drug) will require submission as an SAE. A listing of pregnancies will be presented ([Listing 15](#); [Listing 16](#); [Listing 17](#); [Listing 18](#); and [Listing 19](#)).

9.6. Clinical Laboratory Evaluations

Clinical safety laboratory adverse events will be collected at the time of dosage, at 36 hours post dose (Day 2), Day 5 and Day 12. Chemistry parameters to be evaluated include: total bilirubin, serum albumin, potassium, magnesium, calcium, serum creatinine, blood urea nitrogen (BUN), alkaline phosphatase, alanine aminotransferase (ALT), and aspartate aminotransferase (AST). For patients with severe hepatic impairment an ammonia level will be drawn at screening and will be used as a baseline reading for safety purposes, not as a study entry criterion. Hematology parameters to be evaluated included: hematocrit, hemoglobin, red blood cell count, white blood cell count, automated differential (absolute neutrophils, absolute eosinophils, absolute basophils, absolute lymphocytes, absolute monocytes), and platelet count. The coagulation parameter international normalized ratio (INR) is to be evaluated. Urinalysis parameters to be evaluated by dipstick include: protein, glucose and blood. If any of the urinalysis parameters are positive by dipstick then the sample will be analyzed by reflex microscopy and the results for protein, glucose and blood will be summarized. Grading scales for safety laboratory parameters are presented in [Table 5](#).

The number and percentage of subjects with at least one clinical safety laboratory of mild or greater severity through Day 12 is presented in the overall summary of adverse events ([Table 14](#)).

The distribution of chemistry results by severity, time point, and impairment group will be presented beginning at [Table 26](#) and concluding at [Table 47](#). The distribution of hematology results by severity, time point, and impairment group will be presented beginning at [Table 58](#) and concluding at [Table 79](#). The distribution of urine dipstick results by timepoint and impairment group will be shown in [Table 90](#). The distribution of urinalysis results by severity, time point, and impairment group will be presented in [Table 91](#); [Table 92](#); [Table 93](#); [Table 94](#); [Table 95](#); [Table 96](#); [Table 97](#); and [Table 98](#). The distribution of coagulation results by severity, time point, and impairment group will be presented in [Table 102](#) and [Table 103](#).

Descriptive statistics including mean, standard deviation, median, minimum and maximum values by time point, for each laboratory parameter, will be summarized in [Table 48](#) and concluding at [Table 57](#) (chemistry); [Table 80](#) and concluding at [Table 89](#) (hematology); [Table 99](#) (Urinalysis); and [Table 104](#) (Coagulation). [Table 100](#); and [Table 101](#) will show distribution of categorical urinalysis results. Shift tables will be presented for each laboratory parameter beginning at [Table 105](#) and concluding at [Table 128](#). Change from baseline plots for continuous laboratory parameters will also be presented beginning at [Figure 5](#) and concluding with [Figure 25](#).

[Listing 8](#); [Listing 9](#); [Listing 10](#); and [Listing 11](#) will provide complete listings of individual clinical laboratory results with applicable reference ranges. [Table 22](#); [Table 23](#); [Table 24](#); and [Table 25](#) will provide listings of abnormal laboratory values.

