8 ASSESSMENT OF SAFETY

8.1 Assessing and Recording Safety Parameters

8.1.1 Adverse Events (AEs)

An adverse event is defined as any untoward medical occurrence in a subject regardless of its causal relationship to study treatment. An adverse event can be any unfavorable and unintended sign (including any clinically significant abnormal laboratory test result), symptom, or disease temporally associated with the use of the study drug, whether or not it is considered to be study-drug related. Included in this definition are any newly occurring events or previous condition that has increased in severity or frequency since the administration of study drug.

All adverse events that are observed or reported by the subject during the study (from the time of the first dose of study drug until the Study Day 12 Visit) must be reported, regardless of their relationship to study drug or their clinical significance.

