8.3 Reporting Procedures

AE and SAE reporting is to occur at Visits 01 through 05.

Any medical condition that is present at screening or admission will be considered as pre-existing reported on the Medical History form and will not be reported as an AE. If the severity or frequency of any pre-existing medical condition increases during the study period, then it will be recorded as an AE.

AEs will be followed until resolution even if this extends beyond the study-reporting period. Resolution of an AE is defined as the return to pretreatment status or stabilization of the condition with the expectation that it will remain chronic.

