Diarrhea	2 – 3 loose or watery stools or < 400 gms/24 hours	4 – 5 loose or watery stools or 400 – 800 gms/24 hours	6 or more loose or watery stools or > 800gms/24 hours or requires IV hydration	
LABORATORY ADVERSE EVENTS				
Blood, Serum, or Plasma *				
Potassium – Hypokalemia mmol/L	3.1 – <LLN	2.7 – 3.0	<2.7	
Potassium – Hyperkalemia mmol/L	>ULN – 5.6	>5.6 – 6.5	>6.5	
Glucose – Hypoglycemia Fasting – mg/dL [#]	61 – <LLN	55 – <61	<55	
Glucose – Hyperglycemia Fasting – mg/dL [#]	>ULN – 120	>120 – 130	>130	
Blood Urea Nitrogen mg/dL	>ULN – 29	30 – 35	>35	
Creatinine – mg/dL	>ULN – 1.7	1.8 – 2.0	>2.0	
Calcium – hypocalcemia mg/dL	8.0 – <LLN	7.5 – 7.9	<7.5	

Table 5: Laboratory/Clinical Event Grading Scale (continued)

Category	Mild (Grade 1)	Moderate (Grade 2)	Severe (Grade 3)	Comments
Calcium – hypercalcemia mg/dL	>ULN – 11.0	11.1 – 11.5	>11.5	
Magnesium – hypomagnesemia mg/dL	1.3 – <LLN	1.0 – <1.3	<1.0	
Albumin – Hypoalbuminemia g/dL	2.8 – <LLN	2.5 – 2.7	<2.5	
Alkaline phosphatase – U/L(Age 18 years)	>ULN – 240	241 – 360	>360	
AST U/L	>ULN – 105	106 – 175	>175	
ALT U/L	>ULN – 105	106 – 175	>175	
Bilirubin (serum total) mg/dL	>ULN – 2.0	2.1 – 2.5	>2.5	
Hemoglobin - g/dL	10.5 – <LLN	9.5 – 10.4	< 9.5	
Hematocrit - %	32.3 – <LLN	28.0 – 32.2	< 28.0	
RBC Decrease (Female) X10 ¹² /L	3.61 – <LLN	3.14 – 3.60	< 3.14	
RBC Decrease (Male) X10E6/uL X10 ¹² /L	3.89 – <LLN	3.28 – 3.88	< 3.28	
WBC Increase X10 ⁹ /L	>ULN – 15.0	15.1 – 20.0	> 20.0	
WBC Decrease X10 ⁹ /L	2.5 – <LLN	1.5 – 2.4	< 1.5	
Lymphocytes Decrease - X10 ⁹ /L	0.5 – <LLN	0.3 – 0.4	<0.3	
Neutrophils Decrease - X10 ⁹ /L	1.0 – <LLN	0.5 – 1.0	< 0.5	
Monocytes Increased X10 ⁹ /L	>ULN – 2.5	2.6 – 3.0	>3.0	
Eosinophils Increased X10 ⁹ /L	>ULN – 0.75	0.76-1.50	>1.50	
Basophils Increased X10 ⁹ /L	>ULN – 0.40	0.41 – 0.80	>0. 80	
Platelets Decreased - X10 ⁹ /L	120 – <LLN	100 – 119	<100	
INR	>ULN – 1.3	1.4 – 1.6	>1.6	
Urine *				
Protein	1+	2+	> 2+	
Glucose	Trace – 1+	2+	> 2+	
Blood (microscopic) - red blood cells per high power field (rbc/hpf)	3 – 10	11 – 50	> 50 and/or gross blood	

* The laboratory values provided in the tables serve as guidelines and are dependent upon institutional normal parameters.

* Institutional normal reference ranges should be provided to demonstrate that they are appropriate.

Laboratory Parameter will not be used as halting criteria.

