14.3 Safety Data

14.3.1 Displays of Adverse Events

Table 14: Overall Summary of Adverse Events

Subjects ^a with	Mild Hepatic Impairment (N=X)		Moderate Hepatic Impairment (N=X)		Severe Hepatic Impairment (N=X)		Matched Controls (N=X)		All Subjects (N = X)	
	n	%	n	%	n	%	n	%	n	%
At least one unsolicited adverse event	x	x	x	x	x	x	x	x	x	x
At least one clinical safety laboratory of mild or greater severity through Day 12	x	x	x	x	x	x	x	x	x	x
At least one related unsolicited adverse event	x	x	x	x	x	x	x	x	x	x
Mild (Grade 1)	x	x	x	x	x	x	x	x	x	x
Moderate (Grade 2)	x	x	x	x	x	x	x	x	x	x
Severe (Grade 3)	x	x	x	x	x	x	x	x	x	x
Not yet assessed	x	x	x	x	x	x	x	x	x	x
At least one severe (Grade 3) unsolicited adverse event	x	x	x	x	x	x	x	x	x	x
Related	x	x	x	x	x	x	x	x	x	x
Unrelated	x	x	x	x	x	x	x	x	x	x

Table 14: Overall Summary of Adverse Events (continued)

	Mild Hepatic Impairment (N=X)		Moderate Hepatic Impairment (N=X)		Severe Hepatic Impairment (N=X)		Matched Controls (N=X)		All Subjects (N = X)	
Subjects ^a with	n	%	n	%	n	%	n	%	n	%
At least one serious adverse event ^b	x	x	x	x	x	x	x	x	x	x
At least one related, serious adverse event	x	x	x	x	x	x	x	x	x	x
At least one adverse event leading to early termination ^c	x	x	x	x	x	x	x	x	x	x

N = Number of subjects in the Safety Population

^a Subjects are counted once for each category regardless of the number of events.

^b A listing of Serious Adverse Events is included in Table 18.

^c As reported on the Adverse Event eCRF.

14.3.1.1 **Solicited Adverse Events**

Not Applicable.

14.3.1.2 **Unsolicited Adverse Events**

Table 15: Summary of Unsolicited Adverse Events by MedDRA System Organ Class and Preferred Term, and Impairment Group – Mild Hepatic Impairment

MedDRA System Organ Class	MedDRA Preferred Term	Day 1-5 (N=X)				Day 6-12 (N=X)				Any Time Post Dose (N=X)			
		n	%	95% CI	Events	n	%	95% CI	Events	n	%	95% CI	Events
Any SOC	Any PT	x	xx	xx, xx	x	x	xx	xx, xx	x	x	xx	xx, xx	x
[SOC 1]	Any PT												
	[PT 1]												
	[PT 2]												
[SOC 2]	Any PT												
	[PT 1]												
	[PT 2]												

Note: N = number of subjects in the Safety Population. This table presents number and percentage of subjects. A subject is only counted once per PT/time point.

Tables with similar format:

Table 16: Summary of Unsolicited Adverse Events by MedDRA System Organ Class and Preferred Term, and Impairment Group – Moderate Hepatic Impairment

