14.3.5 Displays of Laboratory Results

14.3.5.1 Chemistry Results

Table 26: Chemistry Laboratory Results by Maximum Severity, Time Point, and Impairment Group – Any Chemistry Parameter

Time Point	Impairment Group	N	None		Mild/ Grade 1		Moderate/ Grade 2		Severe/ Grade 3		Missing	
			n	%	n	%	n	%	n	%	n	%
Baseline	Mild Hepatic Impairment	x	x	xx	x	xx	x	xx	x	xx	x	xx
	Moderate Hepatic Impairment											
	Severe Hepatic Impairment											
	Matched Controls											
Day 2	Mild Hepatic Impairment											
	Moderate Hepatic Impairment											
	Severe Hepatic Impairment											
	Matched Controls											
Day 5	Mild Hepatic Impairment											
	Moderate Hepatic Impairment											
	Severe Hepatic Impairment											
	Matched Controls											
Day 12	Mild Hepatic Impairment											
	Moderate Hepatic Impairment											
	Severe Hepatic Impairment											
	Matched Controls											

Table 26: Chemistry Laboratory Results by Maximum Severity, Time Point, and Impairment Group – Any Chemistry Parameter (continued)

Time Point	Impairment Group	N	None		Mild/ Grade 1		Moderate/ Grade 2		Severe/ Grade 3		Missing	
			n	%	n	%	n	%	n	%	n	%
Max Severity Post Baseline	Mild Hepatic Impairment											
	Moderate Hepatic Impairment											
	Severe Hepatic Impairment											
	Matched Controls											

Note: The “Max Post Baseline” rows indicate the maximum severity experienced by each subject at any time point post baseline, including unscheduled assessments.

N= Number of subjects in the Safety Population with labs available at each visit.

Tables with similar format:

Table 27: Chemistry Laboratory Results by Maximum Severity, Time Point, and Impairment Group – Total Bilirubin

Table 28: Chemistry Laboratory Results by Maximum Severity, Time Point, and Impairment Group – Serum Albumin

Table 29: Chemistry Laboratory Results by Range, Maximum Severity, Time Point, and Impairment Group – Potassium

Time Point	Impairment Group	N	None		Mild/ Grade 1 (Low)		Mild/ Grade 1 (High)		Moderate/ Grade 2 (Low)		Moderate/ Grade 2 (High)		Severe/ Grade 3 (Low)		Severe/ Grade 3 (High)		Missing	
			n	%	n	%	n	%	n	%	n	%	n	%	n	%	n	%
Baseline	Mild Hepatic Impairment	x	x	xx	x	xx	x	xx	x	xx	x	xx	x	xx	x	xx	x	xx
	Moderate Hepatic Impairment																	
	Severe Hepatic Impairment																	
	Matched Controls																	
Day 2	Mild Hepatic Impairment																	
	Moderate Hepatic Impairment																	

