14.3.5.4 Coagulation Results

Table 102: Coagulation Laboratory Results by Maximum Severity, Time Point, and Impairment Group – INR

Time Point	Impairment Group	N	None		Mild/ Grade 1		Moderate/ Grade 2		Severe/ Grade 3		Missing	
			n	%	n	%	n	%	n	%	n	%
Baseline	Mild Hepatic Impairment	x	x	xx	x	xx	x	xx	x	xx	x	xx
	Moderate Hepatic Impairment											
	Severe Hepatic Impairment											
	Matched Controls											
Day 2	Mild Hepatic Impairment											
	Moderate Hepatic Impairment											
	Severe Hepatic Impairment											
	Matched Controls											
Day 5	Mild Hepatic Impairment											
	Moderate Hepatic Impairment											
	Severe Hepatic Impairment											
	Matched Controls											
Day 12	Mild Hepatic Impairment											
	Moderate Hepatic Impairment											
	Severe Hepatic Impairment											
	Matched Controls											

Table 102: Coagulation Laboratory Results by Maximum Severity, Time Point, and Impairment Group – INR (continued)

Time Point	Impairment Group	N	None		Mild/ Grade 1		Moderate/ Grade 2		Severe/ Grade 3		Missing	
			n	%	n	%	n	%	n	%	n	%
Max Severity Post Baseline	Mild Hepatic Impairment											
	Moderate Hepatic Impairment											
	Severe Hepatic Impairment											
	Matched Controls											

Note: The “Max Post Baseline” rows indicate the maximum severity experienced by each subject at any time point post baseline, including unscheduled assessments.

N= Number of subjects in the Safety Population with labs available at each visit.

Table 103: Abnormal Coagulation Laboratory Results Related to Study Treatment by Maximum Severity, Time Point, and Impairment Group – INR

Time Point	Impairment Group	N	Mild/ Grade 1		Moderate/ Grade 2		Severe/ Grade 3	
			n	%	n	%	n	%
Baseline	Mild Hepatic Impairment	x	x	xx	x	xx	x	xx
	Moderate Hepatic Impairment							
	Severe Hepatic Impairment							
	Matched Controls							
Day 2	Mild Hepatic Impairment							
	Moderate Hepatic Impairment							
	Severe Hepatic Impairment							
	Matched Controls							
Day 5	Mild Hepatic Impairment							
	Moderate Hepatic Impairment							
	Severe Hepatic Impairment							
	Matched Controls							
Day 12	Mild Hepatic Impairment							
	Moderate Hepatic Impairment							
	Severe Hepatic Impairment							
	Matched Controls							
Max Severity Post Baseline	Mild Hepatic Impairment							
	Moderate Hepatic Impairment							
	Severe Hepatic Impairment							
	Matched Controls							

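### Table 14's laboratory row counts any graded result, post-dose or not and worsened or not, so it would read about 6 of 6 in the severe group with or without a drug effect (minor)

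*SAP*

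**What the plan says.** SAP 9.6 defines the count as "The number and percentage of subjects with at least one clinical safety laboratory of mild or greater severity through Day 12" and sends it to Table 14, the overall summary of adverse events. The shell repeats the definition: "At least one clinical safety laboratory of mild or greater severity through Day 12". There is an end bound (Day 12), no start bound, and no comparison with baseline. The same section opens with "Clinical safety laboratory adverse events will be collected at the time of dosage" and then adds 36 hours, Day 5 and Day 12, so a sample taken before any drug effect is possible is listed among the laboratory adverse events.

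The protocol's concept of an adverse event is narrower. Section 8.1.1 speaks of "any newly occurring events or previous condition that has increased in severity or frequency since the administration of study drug". Section 8.3 states: "Any medical condition that is present at screening or admission will be considered as pre-existing"; such a condition is not reported as an adverse event. SAP 6.1 already defines baseline, in general, as the last value recorded before study drug.

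**The concern.** Hepatically impaired subjects are enrolled because they have abnormal bilirubin, albumin, INR, ascites or encephalopathy. A row that counts any Grade 1 or higher value therefore counts the entry criterion itself. Safety by impairment group is the secondary objective, and this is the only laboratory line in the overall summary. If it is close to saturated in the severe group from entry values alone, it carries almost no information there, and a reader who sees it under an adverse event heading may take it for a drug effect.

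**Working it through.** The plan states no expected count for this row, so there is no figure to reproduce. The check compares two tables in the documents.

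**Inputs.** Child-Pugh bands are from Protocol Appendix B; grades are from SAP Table 5.

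| Item | Child-Pugh 2 points | Child-Pugh 3 points | Table 5 consequence |
|---|---|---|---|
| INR | 1.7 to 2.3 | above 2.3 | Grade 3 is above 1.6, so 2 or 3 points is always Grade 3 |
| Bilirubin, mg/dL | 2 to 3 | above 3 | Grade 1 ends at 2.0 and Grade 3 is above 2.5, so 2 points is at least Grade 1 (if the ULN is below 2.0) and 3 points is Grade 3 |
| Albumin, g/dL | 2.8 to 3.5 | below 2.8 | 3 points is at least Grade 2; 2 points is graded only if the value is below the laboratory's LLN |

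**Bound for class C.** Class C needs at least 10 points. Encephalopathy and ascites give at most 3 + 3 = 6. The three laboratory items must supply at least 10 − 6 = 4 points, so at least one of them scores 2 or more.

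**Enumeration.** There are 3^5 = 243 score patterns: 6 in class A, 90 in class B, 147 in class C. A pattern is certain to be graded at entry if INR scores 2 or more, or bilirubin scores 2 or more, or albumin scores 3. To count these, remove patterns with no laboratory item at 2 or more, and patterns whose only raised laboratory item is albumin at 2 points.

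- Class C: 147 − 0 − 1 = 146. The exception is encephalopathy 3, ascites 3, bilirubin 1, albumin 2, INR 1. Even that subject is graded if albumin is below the LLN.
- Class B: 90 − 6 − 7 = 77.
- Class A: 6 − 3 − 1 = 2. Nothing is claimed for the mild group.

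If prothrombin time in seconds is scored and INR is ignored, bilirubin at 2 or more or albumin at 3 points still makes 133 of 147 class C patterns certain.

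**Expected count.** With six severe subjects and an assumed probability p of at least one graded result, the expected count is 6p: 5.94 at p = 0.99 and 5.4 at p = 0.90. The probability of exactly 6 of 6 is p^6: 0.94 and 0.53. These values of p are illustrations; the documents give none.

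**Would a post-dose restriction be enough?** No. An entry abnormality that persists to Day 2, 5 or 12 is still counted, so the row stays near 6 of 6. Only a comparison with the subject's own baseline grade removes it; stable entry values then contribute 0 of 6.

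**Limit of that comparison.** A subject already at Grade 3 cannot rise in grade. In class C, INR is certain Grade 3 in 116 of 147 patterns, bilirubin in 66 and both in 49. At least one is at the ceiling in 116 + 66 − 49 = 133, and neither in 147 − 133 = 14.

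**The case against.** The best defence is that the row inherits the protocol's definition. It sits in an adverse event table; Protocol 8.1.1 counts a laboratory result only if clinically significant; inclusion criterion 3 for Groups 1–3 requires entry values judged not clinically significant; and Protocol 10.6.5.1 summarizes events after study product. On that reading an unchanged entry value would not be counted. But the SAP words the row as a graded result, lists it apart from the unsolicited event rows, and does not tie it to those rules. A programmer following SAP 9.6 and the shell would count entry values.

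The second defence is cover elsewhere, and most of it stands. Worsening can be traced through Listings 8–11, the abnormal-value listings (Tables 22–25), the change-from-baseline tables and Figures 5–25, the shift tables, and the related-abnormality tables (37–39 for chemistry, 103 for INR). The shift tables help least, since they use low, normal and high, and a further rise within high does not show. This cover limits the harm; it does not make the Table 14 row informative.

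Third, the link from score to baseline value is looser than a pattern count suggests. The score is set at screening, Protocol 6.1 allows historical information, and the Table 5 footnote says "The laboratory values provided in the tables serve as guidelines and are dependent upon institutional normal parameters". This stands, and is why the result is given as about 6 of 6.

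A reader might also infer that the same fault runs through the results-by-severity tables, such as "Coagulation Laboratory Results by Maximum Severity, Time Point, and Impairment Group" (Table 102) and Tables 26–28. The documents do not support that. Those are tables of results, not adverse events; their summary "rows indicate the maximum severity experienced by each subject at any time point post baseline, including unscheduled assessments"; and each prints a baseline row by grade beside it.

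**Conclusion.** The point holds, as a minor one. As written, the Table 14 laboratory row would read about 6 of 6 in the severe group with or without a drug effect, and it is heavily loaded by entry values in the moderate group (77 of 90 patterns). This rests on unweighted score patterns, on INR being scored, on a bilirubin ULN below 2.0 mg/dL, and on screening values persisting to dosing.

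Two larger conclusions are not supported. One is that the trial's adverse event counts are inflated: the unsolicited, related, severe and serious event rows are separate and unaffected, and Protocol 10.2.2 and 10.6.5 rule out safety hypothesis testing. The other is that the row would manufacture a severe-versus-control difference: the documents give no control rate, and control inclusion criterion 4 lets the investigator accept out-of-range values. What remains is one misleading descriptive count in the summary table.

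**What to change.** 1. In SAP 9.6 and Table 14, restrict the existing laboratory row to post-dose results.
2. Beside it, add a treatment-emergent row: subjects with any post-dose grade through Day 12, unscheduled results included, above their own baseline grade for the same parameter, with baseline as in SAP 6.1.
3. Footnote Table 14 to say that an analyte already at Grade 3 cannot register grade worsening, and refer the reader to the change-from-baseline results for bilirubin (Table 48, Figure 5) and INR (Table 104, Figure 25).
4. In the opening sentence of SAP 9.6, replace *laboratory adverse events* with *laboratory results*.

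Tables 26, 27, 28 and 102 and the shift tables can stay as they are. The cost is a few words, one table row and one footnote. There is no protocol change and no new data, since the values are already collected at admission, Day 2, Day 5 and Day 12. The small downside is that the new row understates worsening in analytes already at Grade 3, which is why the existing row is kept and the footnote added.
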